### 9.2.3 Time to Clinical Response

Time to clinical response (days) is defined as time to the finding of normality (as defined below) for 4 out of 5 vital signs that will be determined upon physical examination. Clinical response is defined as:

- Afebrile with core temperature  $\leq 37.8^{\circ}\text{C}$ , without use of antipyretics (oral  $\leq 37.2^{\circ}\text{C}$ )
- Respiratory rate  $\leq 24$  beats per minute
- Oxygen saturation  $\geq 95\%$  on room air without support or a return to pre-infection status, if pre-infection status was  $< 95\%$
- Pulse rate  $\leq 100/\text{min}$
- SBP  $\geq 90$  mm/Hg, without vasopressor use

For determination of time to clinical response, achievement of any of the criteria above will carry forward to missing data at subsequent visits. Subjects who do not experience clinical response will be censored at the last available vital sign visit date. Time to Clinical response will be analyzed using Kaplan-Meier techniques.

Pre-infection oxygen saturation data on room air status was not collected on the CRF. Therefore, prior to database lock, for any subject with persistent oxygen saturation on room air  $< 95\%$ , a query to the investigator will be sent to request historic oxygen saturation on room air data. If a baseline oxygen saturation on room air value collected during 6 months prior to enrollment is available, the information will be captured and recorded in a spreadsheet maintained by data management at POI. This spreadsheet will be reviewed, signed and locked prior to database lock. This information will be used to define pre-infection oxygen saturation on room air for the purposes of calculating time to clinical response. If there are no available medical record data and oxygen saturation remains below 95% on room air, the subject will be analyzed as not experiencing clinical response.

Note, the number of vital signs abnormalities (utilizing the above criteria) may range from 0 to 5 for subjects enrolled in the trial, although the expectation is that all subjects will have at least one abnormality. Therefore, this analysis will be conducted in two ways. First, the probability of time to clinical response (defined as the finding of at least 4 of 5 normal vital signs using the criteria above) will be calculated via Kaplan-Meier; under this analysis, some subjects will have met criteria for a clinical response at baseline. Time to clinical response will be calculated as Date of

January 17, 2019

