Event – Date of Day 1. If the event was not achieved then the value will be censored and calculated as Date of the last available assessment – Date of Day 1. P-values for each VIS410 dose versus placebo, VIS401 total versus placebo and for VIS410 4000 mg versus 2000 mg will be presented. The number and percentage of subjects in each treatment group with clinical response will be summarized. Results will be presented graphically as well.

This analysis will be repeated for subjects with >2 vital signs abnormalities at baseline, using the same analysis algorithm described above; under this analysis, no subject will meet criteria for clinical response at baseline.

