## 16.6 List of Proposed Tables, Figures, and Listings

### 16.6.1 Tables

Table	Title	Population
14.1.1.1	Subject Disposition	ITT
14.1.1.2	Subject Disposition	MITT
14.1.1.3	Subject Disposition by Region and Site	ITT
14.1.2.1	Summary of Protocol Deviations	ITT
14.1.3.1	Demographics and Baseline Characteristics	ITT
14.1.3.2	Demographics and Baseline Characteristics	MITT
14.1.4.1	Medical History	ITT
14.1.4.2	Medical History	MITT
14.1.5.1	Prior Medications	ITT
14.1.5.2	Prior Medications	MITT
14.1.6.1	Concomitant Medications	Safety
14.1.7.1	Treatment Exposure and Compliance	Safety
14.1.7.2	Treatment Exposure and Compliance	MITT
14.2.1.1.1	Summary of Clinical Outcome on Seven-Level Ordinal Scale through Day 14	MITT
14.2.1.1.2	Summary of Clinical Outcome on Five-Level Modified Ordinal Scale through Day 14	MITT
14.2.1.1.3	Summary of Clinical Outcome on Seven-Level Ordinal Scale through Day 14 Sensitivity Analysis	MITT
14.2.1.2	Summary of Area Under the Curve for Seven-Level Ordinal Scale	MITT
14.2.1.3	Summary of Area Under the Curve for Seven-Level Ordinal Scale Excluding Death Outcome	MITT
14.2.1.4	Summary of Area Under the Curve based on Modified Five-Level Ordinal Scale	MITT
14.2.1.5	Summary of Area Under the Curve for Seven-Level Ordinal Scale Sensitivity Analysis	MITT
14.2.1.6	Additional Assessments for Seven-Level Ordinal Scale	MITT
14.2.1.7	Additional Assessments for Seven-Level Ordinal Scale Sensitivity Analysis	MITT
14.2.1.8	Summary of Proportions of Best and Worst Cases for Seven-Level and Modified Five-Level Ordinal Scale	MITT
14.2.2.1	Time to Cessation of O2 Support	MITT
14.2.3.1.1	Kaplan-Meier Estimates of Time to Clinical Response (Resolution of Vital Signs)	MITT
14.2.3.1.2	Kaplan-Meier Estimates of Time to Clinical Response (Resolution of Vital Signs) in Subjects with > 2 Vital Sign Abnormalities at Baseline	MITT

14.2.3.1.3	Kaplan-Meier Estimates of Time to Complete Clinical Response (Resolution of Vital Signs)	MITT
14.2.3.1.4	Kaplan-Meier Estimates of Time to Complete Clinical Response (Resolution of Vital Signs) in Subjects with >2 Vital Sign Abnormalities at Baseline	MITT
14.2.4.1	Kaplan-Meier Estimates of Time to Cessation of Ventilator Support	MITT
14.2.5.1	Summary of Healthcare Resource Utilization Parameters	MITT
14.2.5.2	Summary of Visual Analogue Scale Scores	MITT
14.2.6.1.1	Descriptive Summary of FluPRO Domain Scores, Component Scores, and Total Score	MITT

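### The repeat time-to-clinical-response analysis requires more than 2 abnormal baseline signs although 2 already rules out response, so it leaves out some subjects who are still at risk

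*SAP*

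**What the plan says.** SAP 9.2.3 lists five criteria (temperature, respiratory rate, oxygen saturation, pulse, systolic pressure). For its Kaplan-Meier analysis it takes response as "defined as the finding of at least 4 of 5 normal vital signs using the criteria above". It notes that at enrolment "the number of vital signs abnormalities (utilizing the above criteria) may range from 0 to 5", while expecting every subject to have at least one, and so runs the analysis twice.

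The first run uses the MITT population. The SAP acknowledges its weakness: "under this analysis, some subjects will have met criteria for a clinical response at baseline". The second run is described in one sentence. It opens "This analysis will be repeated for subjects with >2 vital signs abnormalities at baseline", keeps the same algorithm, and ends with the property "no subject will meet criteria for clinical response at baseline".

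The list of tables in SAP 16.6.1 carries the cut-off into the title of Table 14.2.3.1.2, which ends "in Subjects with > 2 Vital Sign Abnormalities at Baseline". The same cut-off appears in Table 14.2.3.1.4 and Figure 14.2.1.1.3, but those outputs are for a complete clinical response, which 9.2.3 does not define. Protocol 10.6.3 specifies the Kaplan-Meier analysis and log-rank tests without any such subset.

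**The concern.** The second run is there to deal with the subjects who count as responders at time zero in the first. The natural population is therefore everyone who is not a responder at baseline. The cut-off in 9.2.3 is one step stricter than the response definition requires, and the SAP gives no reason for the extra step. SAP 4.3 lists no subgroup by number of abnormal signs, and SAP 16.1 does not mention the restriction among the changes from the protocol.

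At stake is the amount of information in the repeat. SAP 2.2 says the trial's tests are meant to show which endpoints deserve to go into Phase 3. With about 40 subjects per arm, removing at-risk subjects from the analysis that is free of baseline responders costs events, and could make this endpoint look less sensitive than it is. It also shifts the repeat towards sicker patients without saying so.

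**Working it through.** **Inputs.** Response requires at least 4 of 5 normal signs (SAP 9.2.3). The repeat requires more than 2 abnormal signs, that is, 3 or more (SAP 9.2.3). Planned size is about 120 (SAP 2.3). The baseline distribution of abnormal signs is not given.

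**Step 1: the definition, counted out.** With *a* abnormal signs, 5 − *a* are normal, and the subject is a responder if 5 − *a* ≥ 4, i.e. *a* ≤ 1. There are 2⁵ = 32 normal/abnormal patterns.

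| Abnormal | Normal | Patterns | Responder at baseline? | In the >2 subset? |
|---|---|---|---|---|
| 0 | 5 | 1 | yes | no |
| 1 | 4 | 5 | yes | no |
| 2 | 3 | 10 | **no** | **no** |
| 3 | 2 | 10 | no | yes |
| 4 | 1 | 5 | no | yes |
| 5 | 0 | 1 | no | yes |

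**Step 2: the SAP's own statement.** Under >2, none of the 10 + 5 + 1 = 16 patterns is a responder. The statement is true.

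**Step 3: the smallest cut-off with the same property.** Under ≥2, none of the 10 + 10 + 5 + 1 = 26 patterns is a responder. Under ≥1, five patterns are. So ≥2 is the least restrictive cut-off that works, and >2 removes the 10 non-responder patterns with exactly two abnormal signs. These are counts of patterns, not of patients.

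**Step 4: missing signs.** If a sign may also be missing, a subject with two recorded abnormalities has at most three signs left that could be normal. Even if every missing sign is counted as normal, none of the 131 patterns with at least two recorded abnormalities reaches four.

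**Step 5: possible size, by assumption only.** Suppose the saturation criterion fails in every subject. That fits the oxygen-support requirement in protocol 5.2.1 (criterion 4) and the SAP's expectation of at least one abnormality each. Suppose also that each of the other four signs is independently abnormal with probability *q*. Then P(exactly 2) = 4*q*(1 − *q*)³ and P(≥2) = 1 − (1 − *q*)⁴.

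| *q* | P(exactly 2) | P(≥2) | Share of baseline non-responders left out | Left out, of 120 |
|---|---|---|---|---|
| 0.2 | 0.410 | 0.590 | 69% | 49 |
| 0.3 | 0.412 | 0.760 | 54% | 49 |
| 0.4 | 0.346 | 0.870 | 40% | 41 |
| 0.5 | 0.250 | 0.938 | 27% | 30 |

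Letting saturation be abnormal in only 80% to 100% of subjects widens the range of shares slightly, to 27%–70%. Neither *q* nor independence comes from the documents.

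**The case against.** The strongest reply is that nothing in 9.2.3 is false. The SAP says that nobody in the >2 subset responds at baseline, which is correct, and it never claims that >2 is the minimum needed. A reader might infer a proven slip of one. The documents do not establish that. The same cut-off is reused for the complete-response outputs. If complete response means all five signs normal, one abnormal sign already rules it out at baseline, so >2 there is not a simple one-step miscount. A common, more abnormal subset applied to both endpoints would explain the text equally well. What remains is that no such purpose is written down, and the one stated property does not need >2.

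A reader might also infer that these subjects are lost to the endpoint, or that the comparison is biased. Neither follows. They stay in the first Kaplan-Meier analysis, which is the one the protocol specifies. Baseline is defined in SAP 4.1 as preceding study drug, so either cut-off gives a subset fixed before treatment. Nor does the SAP rank the repeat above the MITT run, so calling it the only interpretable version would go too far.

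Finally, the endpoint is secondary, the study is declared unpowered, and SAP 4.1 treats p-values as informational. That limits the importance of the point but does not supply a reason for the stricter cut-off.

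**Conclusion.** The point holds as a matter of counting. On the SAP's own definition, two abnormal signs exclude response at baseline, and the >2 cut-off leaves subjects with exactly two out of the repeat analysis although they can still have the event. The consequence is lost precision and a somewhat sicker population in a supplementary analysis of a secondary endpoint. There is no bias, and the primary Day 7 ordinal analysis is untouched.

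The size cannot be established from the documents. The shares in step 5 show only that the group need not be small; they rest on assumed frequencies and on independence between signs, and correlated signs would change them. The word unnecessary is justified only against the purpose the SAP states. If a severity subset was intended, the fault is that the SAP does not say so.

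**What to change.** For the 4-of-5 endpoint, change the cut-off to ≥2 in SAP 9.2.3 and in the title of Table 14.2.3.1.2. If a sicker subset is also wanted, keep >2 as an additional analysis, label it as a severity subset and give the reason.

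Do not replace the symbol everywhere. Table 14.2.3.1.4 and Figure 14.2.1.1.3 concern complete clinical response. Define that endpoint in 9.2.3 first, then set its baseline cut-off from the definition: ≥1 if it means all five signs normal.

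The cost for the 4-of-5 endpoint is a short text edit, one table title and one filter condition; the complete-response outputs also need a definition. No new data are required. Make the change before unblinding. If that point has passed, report the ≥2 analysis beside the planned one and document it in the clinical study report, as SAP 4.1 requires for departures from the plan. In either case, report the number of subjects per arm at each baseline count from 0 to 5, so that the size of the excluded group can be seen.

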#### **9.2.4 Time to cessation of ventilator support**

Based on data from subjects on O2 support at baseline, the probability of time to cessation of ventilator support will be calculated via Kaplan-Meier based on ordinal scale data. Time to cessation of ventilator support will be calculated as Date of Event – Date of Day 1. If the event is not achieved then the value will be censored and calculated as Date of the last available ordinal assessment – Day 1. P-values for each VIS410 dose versus placebo, VIS410 total versus placebo and for VIS410 4000 mg versus 2000 mg will be presented. Results will be presented graphically as well.

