1.0 INTRODUCTION

1.1 Background Information

Severe influenza disease is a common occurrence each season, especially in high-risk groups, such as young children, older adults, patients with pulmonary conditions, inflammatory conditions, malignancies, and pregnant women.^{1,2} Despite available therapy with neuraminidase inhibitors, including oseltamivir (Tamiflu[®]), zanamivir (Relenza[®]), and peramivir (Rapivab[®]), 10% to 44% of hospitalized patients require intensive care and 25% to 50% of these patients die. It is estimated that as many as 400,000 patients are hospitalized with influenza each year in the United States, with up to 49,000 deaths per year.³

The World Health Organization (WHO) has reported incidence rates of 3 to 5 million severe cases and about 250,000 to 500,000 influenza-related deaths annually.⁴ The 2009 influenza A pandemic (H1N1) spread rapidly to every continent with more than 399,232 reported cases and 4735 deaths.⁵

The therapeutic use of passive polyclonal antibodies to prevent viral infections, including hepatitis B, varicella, cytomegalovirus, rabies, and respiratory syncytial virus (RSV) has been well established. More recently, monoclonal antibodies for viral infections have been developed, including palivizumab (Synagis[®]), a Food and Drug Administration (FDA)-licensed treatment for the prevention of RSV infection.

Visterra has developed a novel approach to antibody discovery whereby functionally conserved epitopes are identified based on atomic interaction networks and targeted with rationally engineered human antibodies. Using this approach, VIS410, a broad spectrum human immunoglobulin G1 (IgG1) monoclonal antibody with demonstrated efficacy against both Group 1 (including H1 and H5) and Group 2 (including H3 and H7) influenza A strains, in both treatment and prevention models of influenza, was developed. Visterra intends to develop this product for the treatment of influenza A, specifically in hospitalized patients.

This study will provide the first indications of efficacy, safety, and tolerability of VIS410 in hospitalized subjects with influenza A infection requiring oxygen support. Efficacy will be assessed by comparison of clinical status ordinal Day 7 scores between treatment groups.

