5.2.1 Inclusion Criteria

Subjects meeting all of the following criteria are eligible to participate in this study:

1. Male and female subjects aged ≥ 18 years. For a country where the legal age of consent is >18 years old, the country requirements should be followed.
2. Test positive for influenza A by rapid antigen test or with another commercially available test on an adequate nasopharyngeal specimen in accordance with the manufacturer's instructions, or an acceptable local test including, PCR, FIA, or ELISA.
3. Onset of influenza symptoms no more than 5 days before VIS410/placebo infusion; symptoms may include cough, dyspnea, sore throat, fever, myalgias, headache, nasal symptoms (rhinorrhea, congestion), fatigue, diarrhea, anorexia, nausea, and vomiting.
4. Requirement for oxygen support including any positive pressure ventilation (PPV).
5. Women of childbearing potential must have a negative pregnancy test within 2 days prior to VIS410/placebo infusion.
6. Women should fulfill one of the following criteria:
 - a. Post-menopausal: either amenorrhea ≥ 12 months or follicle stimulating hormone > 40 mIU/mL as documented in their medical history
 - b. Surgically sterile; hysterectomy, bilateral oophorectomy, or tubal ligation
 - c. Women of childbearing potential participating in heterosexual relations must be willing to use adequate contraception from screening until 60 days post-VIS410/placebo infusion (see Section 6.2).
7. Non-vasectomized (or vasectomized less than 6 months prior to dosing) male subjects who have a female partner of childbearing potential must use an effective birth control method (see Section 6.2) when having heterosexual intercourse, from screening until 60 days post-VIS410/placebo infusion.
8. Subject is able and willing to comply with study procedures, as per protocol.
9. Subject, or a legally acceptable representative, is able to understand the purpose and risks of the study and willing to give voluntary written informed consent.

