### 2.4.2 Secondary Objectives

Each of the following objectives will be assessed in the following pairings; 4000mg vs placebo, 2000mg vs placebo, pooled 4000mg+2000mg vs placebo and 4000mg vs 2000mg

January 17, 2019

- Among subjects requiring supplemental oxygen therapy at the time of enrollment with baseline room air oxygen saturation of  $\leq 92\%$ , time to cessation of oxygen (O2) support resulting in stable oxygen saturation (SpO2) by pulse oximetry. Stable SpO2 is defined as two consecutive SpO2 values of  $> 92\%$  on room air that are at least 8 hours apart.
- For any subject requiring supplemental oxygen therapy at the time of enrollment (regardless of oxygen saturation), time to cessation of oxygen support.
- Evaluate the effect of 2 dose levels of VIS410 + oseltamivir vs oseltamivir alone on the following parameters, also examine these outcomes in pooled VIS410 + oseltamivir arms vs oseltamivir alone:
  - Assess Viral load parameters in upper respiratory samples (MITT population and subsets)
  - Time to clinical response
  - Time to cessation of ventilator support
  - Time to resumption of normal activities
  - All-cause and attributable Day 14, Day 28, and Day 56 mortality rates
  - Clinical status ordinal scale mean area under the curve for Days 1-7 and Days 1-14 using linear numeric scores for the ordinal categories.
  - Comparison of clinical status ordinal scale scores
  - Comparison of clinical status ordinal scale scores using modified ordinal scale criteria (i.e., pooling of selected severity criteria scores)
  - Comparison of discrete ordinal scale parameters, including days of ventilator support, days in intensive care, and duration of hospitalization
  - Healthcare resource utilization
  - Analysis of time to alleviation of clinical signs and symptoms of influenza in the subset of subjects able to complete the Influenza Subject Reported Outcomes (FluPRO) Questionnaire at baseline and post-dose by Kaplan Meier analysis
  - Comparison of mean overall FluPRO scores by day and treatment arm, and mean FluPro Domain scores by day and treatment arm.
  - Proportion of subjects with newly documented bacterial pneumonia/superinfection
  - Proportion of subjects with influenza-related complications
- Pharmacokinetics of VIS410 in serum
- Immunogenicity of VIS410
- Emergence of resistance to VIS410 and oseltamivir

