## 4 GENERAL ANALYSIS DEFINITION

### 4.1 General Considerations

All statistical analyses and summary information are to be generated according to this SAP. Any deviations from this SAP will be documented in the clinical study report (CSR).

These descriptive statistics will be presented for continuous parameters: the number of subjects used in the calculation (n), mean, standard deviation (SD), median, minimum, and maximum values. For PK parameters, the geometric mean and coefficient of variance (CV) will also be presented. All continuous summaries will display the minimum and maximum value with the same number of decimals collected in the data. The median, mean, geometric mean and CV will display 1 additional decimal, and the SD and SE will display 2 additional decimals. For categorical variables, frequencies and percentages will be reported. All percentages will be reported to 1 decimal; all p-values will be reported to 3 decimals.

All temperature measurements will be presented as degrees Celsius. Degrees in Fahrenheit will be converted with this formula:

$$T_C = (T_F - 32) * (5/9),$$

where  $T_C$  is a Celsius temperature and  $T_F$  is a Fahrenheit measurement.

Since this is a phase 2 study rigorous control over type 1 error will not be used; all statistical comparisons will be performed using 2-sided tests at the 0.05 significance level, unless specifically stated otherwise. All null hypotheses will be defined as no treatment difference. All p-values are presented for informational purposes only; there will not be any adjustments for multiple comparisons.

All analyses, summary tables, figures, and data listings will be generated with SAS version 9.4 or higher. Specialized PK software will be used for some PK analyses.

Baseline is defined as the latest non-missing measurement taken prior to study drug administration.

January 17, 2019

All summaries will be by actual visit, no visit windows for analysis will be defined. In general, summaries will be by treatment groups, and will include a combined VIS410 treatment group, in addition to the individual low dose (2000 mg) VIS410, high dose (4000 mg) VIS410, and Placebo treatment groups, unless specified differently. Summaries of disposition, other baseline data, and adverse events will also include an overall column.

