## 4.3 Subgroups

The following subgroups may be used to provide further information on the primary efficacy endpoint and other clinical and virologic endpoints:

- Use of positive pressure ventilation
- Use of endotracheal intubation
- Time from onset of symptoms to VIS410 therapy
- Number of oseltamivir doses prior to VIS410
- Age categorization (<65 years, ≥65 years)
- Presence of underlying chronic lung disease
- Presence of coincident pneumonitis (pneumonia) at baseline
- Influenza A subtype
- Enrollment geographic region: Tiered assessments: initially, dichotomous (Northern Hemisphere and Southern Hemisphere), then with each hemisphere broken into two groups: North America (Canada and US) and Europe (Belarus, Belgium, Bulgaria, Estonia, France, Georgia, Latvia, Russia, Serbia, Spain, Ukraine and Georgia); and Asia/Oceania (Australia, Malaysia, New Zealand, Singapore, and Thailand) and South Africa. Enrollment geographic region: (northern hemisphere vs southern hemisphere)
- MITT subset comprised of subjects with positive baseline viral cultures based on TCID50
- Baseline HAI titer category (to matched virus subtype) (≤40 or >40)
- Time between onset of symptoms of influenza and treatment (< 72 hours or ≥ 72 hours)

January 17, 2019

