-  During hospitalization, body temperature will be recorded at the end of infusion on Day 1 then BID up until Day 14 or discharge from the hospital if discharge occurs prior to Day 14. In cases where obtaining oral temperature is not possible, core temperature will be obtained. While hospitalized, the maximum temperature should be recorded for each 12-hour interval (from 12 AM to 12 PM and from 12 PM to 12 AM).
-  Additional targeted physical exam may be performed throughout the study as needed at the Investigator's or his/her designee's discretion.
-  The Influenza Patient Reported Outcomes (FluPRO) Questionnaire (Appendix 14.1) must be completed (ie, self-reported) by the subject at baseline (Day 1) and daily thereafter through Day 14. Subjects who are not able to complete the questionnaire at baseline (Day 1) will be exempt from this assessment throughout the study. The FluPRO will be completed at home for subjects that are discharged from the hospital prior to Day 14.
-  The ordinal scale will be completed from baseline (Day 1) and daily thereafter through Day 14. For each day, subjects will be classified by the worst clinical outcome for which they qualify.
-  A urine or serum pregnancy test must be performed at screening locally (ie, by the investigative site) within 2 days prior to dosing. Negative results must be obtained prior to randomization.
-  A serum pregnancy test will be performed at the central lab for all female subjects of childbearing potential following randomization at baseline.
-  Subjects to be enrolled based on the Investigator's discretion including any local laboratory results per SOC at institution.
-  See Laboratory Assessments for list of tests to be performed by the Central Lab in Appendix 14.2.
-  Serum creatinine to be done locally within 24 hours prior to randomization, the result is required for oseltamivir dosing.
- 20a ESR to be performed locally.
-  A chest x-ray or computed tomography (CT) scan taken per SOC within 72 hours before dosing is acceptable.
-  Healthcare utilization (total length of hospital stay, length of ICU stay, and rehospitalization) will be captured through the last follow-up visit.

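### SAP 9.2.4 analyses time to cessation of ventilator support in everyone on oxygen at baseline and does not define the event, so the curve does not estimate time to coming off a ventilator

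*SAP*

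**What the plan says.** Among the secondary objectives, SAP 2.4.2 lists "Time to cessation of ventilator support". SAP 9.2.4 gives the method: "Based on data from subjects on O2 support at baseline, the probability of time to cessation of ventilator support will be calculated via Kaplan-Meier", using the ordinal scale data. Time runs from Day 1 for every subject. The only rule for subjects without the event is: "If the event is not achieved then the value will be censored and calculated as Date of the last available ordinal assessment", minus Day 1. Four p-values are planned: each dose against placebo, pooled VIS410 against placebo, and one dose against the other. Table 14.2.4.1 and Figure 14.2.2.1 both carry the population label MITT.

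The surrounding text does not narrow the set:

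- Protocol 5.2.1, criterion 4, requires oxygen support of every subject and treats positive pressure ventilation (PPV) as one form of it.
- SAP 2.1 stratifies randomisation by PPV present or absent, so non-ventilated subjects are expected.
- Protocol 10.6.4 names Kaplan-Meier and the log-rank test but no at-risk set.
- SAP 16.1 records no change for this endpoint.
- SAP 4.3 includes PPV use and intubation, but only as an option: "The following subgroups may be used to provide further information on the primary efficacy endpoint and other clinical and virologic endpoints".

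On the ordinal scale, score 6 is an ICU stay with mechanical ventilation and score 7 is death. The schedule footnote says: "The ordinal scale will be completed from baseline (Day 1) and daily thereafter through Day 14".

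**The concern.** A subject who is not on a ventilator cannot come off one, so an analysis of time to cessation should start from subjects who are ventilated. Section 9.2.4 starts from subjects on oxygen, and it does not say which change in ordinal score counts as the event. The treatment of never-ventilated subjects, possibly most of the set, is then left to the programmer.

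Death is also left open. Nothing in 9.2.4 says that a move from score 6 to 7 is not cessation. SAP 9.1 states the carry-forward of score 7 only for deaths before Day 7.

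What is at stake is interpretation. The trial's stated use of significance testing is to compare the strength of evidence across endpoints and choose candidates for Phase 3 (Protocol 10.1, SAP 2.2). A diluted or reversed ventilator result would misinform that choice.

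**Working it through.** The plan gives no event count or power for this endpoint, so there is no figure of its own to reproduce.

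**Inputs.** 120 subjects, 40 per arm (SAP 2.1). Follow-up is 14 − 1 = 13 days. The ventilated share is an assumption. The nearest figure, in Protocol 1.1, is "10% to 44% of hospitalized patients require intensive care and 25% to 50% of these patients die". That is intensive-care need, not ventilation, so 10% to 44% is only a working range: 0.10 × 120 = 12 to 0.44 × 120 ≈ 53 subjects.

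**Step 1: the Day 14 estimate.** Take N subjects in an arm, v ventilated at baseline and c of them off by Day 14, with no later ventilation, no deaths and complete ordinal data. Nobody is censored before Day 14, so the Kaplan-Meier cessation estimates are simple proportions:

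- ventilated only: c/v
- never-ventilated censored: c/N
- never-ventilated counted at Day 0: (c + N − v)/N

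| v of 40 | c | Ventilated only | Censored | Day 0 events |
|---|---|---|---|---|
| 4 | 3 | 3/4 = 75% | 3/40 = 7.5% | 39/40 = 97.5% |
| 10 | 8 | 8/10 = 80% | 8/40 = 20% | 38/40 = 95% |
| 18 | 14 | 14/18 = 78% | 14/40 = 35% | 36/40 = 90% |

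**Step 2: the shape of the curve.** With censoring, the proportion still ventilated cannot fall below 1 − v/N. At 10/20/30/44% ventilated the floor is 90/80/70/56%, even if every ventilated subject is weaned. The median is not reached in any arm where fewer than half are ever ventilated. With Day 0 coding, more than half the arm has the event at time zero in the same cases, so the median is zero.

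**Step 3: the test.** Simulation of pooled VIS410 (80) against placebo (40). Assumptions: exponential weaning times in whole days, placebo median 7 days, true weaning hazard ratio 2, two-sided log-rank at 0.05.

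| Ventilated at baseline | Censored | Day 0 events | Ventilated only |
|---|---|---|---|
| 12 | 0.2% | 0.2% | 16% |
| 24 | 0.5% | 6% | 28% |
| 36 | 1.4% | 14% | 40% |
| 53 | 8% | 24% | 57% |

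Fifty-three does not divide 1:2. The last row matches a split of 17 placebo and 36 VIS410. With 18 and 35, the censored figure is about 3% and the Day 0 figure is higher, though still below the ventilated-only figure. With no true effect and balanced arms, the censored analysis rejects in at most about 0.3% of runs, against about 5% to 6% in ventilated subjects only.

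**Step 4: new ventilation under the censoring rule.** Take 40 subjects, 10 ventilated at baseline and 30 not. Suppose 20% of the 30 (6) are later ventilated in one arm and 10% (3) in the other, and everyone ventilated is weaned by Day 14. The curve then shows cessation in 16/40 = 40% and 13/40 = 32.5%. The arm with fewer new ventilations looks slower.

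A large-sample simulation used the same 20% (placebo) and 10% (VIS410), no weaning effect, and first ventilation on Days 2 to 6. It gave a cessation rate ratio of about 0.67/0.78/0.89 at 10/20/44% ventilated. The 20% and 10% are assumptions with no source in the documents.

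**The case against.** The strongest reply is that 9.2.4 never defines the event, so it is too much to say that the plan censors never-ventilated subjects. SAP 9.2.3 accepts that some subjects meet its criterion at baseline, and by analogy never-ventilated subjects would be Day 0 events here. The output shells, in a separate document, might settle it. This stands: censoring is the only rule written, but it is one reading of two. It does not rescue the section, because Day 0 coding also dilutes the comparison and fills the curve with weanings that never happened.

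Several other points stand:

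- The study is not powered for any outcome, and SAP 4.1 says: "All p-values are presented for informational purposes only; there will not be any adjustments for multiple comparisons". Loss of power alone therefore carries little weight.
- No hazard or rate ratio is planned for this endpoint, so the ratio in Step 4 shows direction and is not a planned output.
- Ventilator days (9.2.1), hours on ventilation (9.2.5), a ventilator-support listing and the optional subgroups already give a reader some protection.
- Each day is classified by the worst outcome, so a subject who died on Day 7 or later should still score 7 afterwards. The death issue is a gap in wording, not a shown error.

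A reader might infer that the test would give false positives, or that VIS410 would be shown as harmful. The documents support neither. With ventilated subjects balanced across arms, which PPV stratification favours, the censored test rejects too rarely. The reversal in Step 4 needs a difference in new ventilation that the documents do not predict.

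**Conclusion.** The point holds in this form: the at-risk set is wrong for the endpoint and the event is undefined. Under either available reading, the curve and its four p-values do not estimate time to coming off a ventilator.

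The dilution in Step 1 is arithmetic once the ventilated share is fixed. The share itself, the weaning times, the hazard ratio of 2 and the later-ventilation rates are all assumptions, and the true ventilated share could lie below 10%. The direction of the problem does not depend on them. Its size does.

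The consequence is a misleading supportive analysis. Time to cessation of ventilator support is an objective in SAP 2.4.2 but is not among the endpoints listed in SAP 3.2. It would be wrong to read this as a threat to the Day 7 ordinal analysis, which is unaffected. The section should be corrected because the correction is cheap and the results are meant to inform the choice of Phase 3 endpoints.

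**What to change.** In SAP 9.2.4, Table 14.2.4.1 and Figure 14.2.2.1:

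1. Restrict the analysis to MITT subjects on mechanical ventilation at baseline, and say how that status is read. A Day 1 score of 6 would match the event definition below.
2. Define the event as the first move from ordinal score 6 to a score of 5 or lower. The ordinal data can remain the source. The ventilation start and stop times that Protocol 6.3.3 places in EDC may serve as a check.
3. State that death (score 7) is not cessation, and keep every death as a non-event to Day 14 whatever the day of death.
4. Describe subjects first ventilated after Day 1 through the ventilator-day comparison in 9.2.1 and the hours on ventilation in 9.2.5, both already planned.

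The cost is wording and a subset flag, with no new data. The downside is a small, weakly powered subset, about 12 to 53 of 120 under the assumed range, which leaves out subjects first ventilated after Day 1.
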